Sponsor: PROMOMED RUS LLC, Russia	Separate study table relating to part of the dossier	(For use by national authorized bodies only)
Name of finished product: Areplivir, film-coated tablets	Volume: Pages:	
Active ingredient: Favipiravir		
Investigational medicinal product, dose and mode of administration, batch number: Investigational medicinal product: Areplivir, film coated tablets (PROMOMED RUS LLC, Russia), batch 010520 (expiry date 06.2022). Patients in Arm 1 take the investigational product Areplivir, film coated tablets: on Day 1st of treatment - 1600 mg (8 tablets) 2 times a day; on days 2-14 of treatment - 600 mg (3 tablets) 2 times a day. The drug is taken orally every 12 hours, swallowing whole tablet without chewing and washing down with a glass of water. The course of treatment is 14 days. The test drug is administered in hospital setting under supervision of a clinical investigator. The test drug is not handed over to the patient.		
Duration of the study: The total duration of the study for the patient is not more than 31 days, of which the screening period is not more than 2 days. Visits: Visit 0 (screening, not more than 2 days); Visit 1 (randomization, day 1)*; Visit 2 (day 5); Visit 3 (day 10); Visit 4 (day 15)**; Visit 5 (day 21±1)***; Visit 6 (study completion, day 28±1)***. * Visit 1 may coincide with Visit 0. ** If a patient is discharged from hospital at an earlier date, the visit will be conducted at the time of discharge (for Arm 2 patients). *** If a patient is discharged from hospital at an earlier date, then this patient does not need to visit the study site. Fatalities and serious adverse events (SAE) will be followed-up through telephone contact with the patient. Discharge of patients from a hospital is carried out in accordance with the local practice of the study site in compliance with the current sanitary and epidemiological regime.		
Efficacy criteria: The efficacy of therapy is assessed using the following endpoints: Primary efficacy criterion: 
 • Time (in days) to improvement in clinical status by categorical ordinal scale of clinical status improvement. • Rate of clinical status improvement by categorical ordinal scale of clinical status improvement by 2 or more categories at Visit 3. Secondary efficacy criteria:		

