- Percentage of cases with non-invasive lung ventilation.
- Percentage of cases with mechanical lung ventilation.
- Incidence of fatal cases.
- Assessment of lung injury according to CT data at Visits 4, 5 and 6.**

* Virus elimination is defined as two negative laboratory tests for SARS-CoV-2 RNA obtained at intervals of 24 hours.

**An "empirical" visual scale will be used to estimate changes in lung involvement from CT data.

For the analysis of these parameters, an intergroup comparison of shares is used using a two-sided version of the **Fischer's exact test** (or a two-sided version of the χ^2 (chi-square) test, if all the expected values in the cells of the contingency table for this analysis are 5 or more).

The protocol also includes the following endpoint:

- Time (in days) to fever disappearance (body temperature < 37.2 ° C for 3 consecutive days

Sponsor: PROMOMED RUS LLC, Russia	Separate study table relating to part of the dossier	(For use by national authorized bodies only)
Name of finished product: Areplivir, film-coated tablets	Volume: Pages:	
Active ingredient: Favipiravir		

without antipyretic medication).

For the secondary efficacy parameter "time (in days) to fever disappearance (body temperature < 37.2 °C for 3 consecutive days without antipyretic drugs), a comparison between arms is made using the *Student's t-test* or the *Mann-Whitney test* (depending on the nature of the distribution of quantitative indicators). Also, *Kaplan-Meier technique* and the construction of *survival tables* can be used as descriptive methods of study. The *Gehan-Wilcoxon test, the Cox-Mentel test or the Log-Rank test* can be used to compare the time (in days) to the disappearance of fever in the study arms.

Analysis of secondary efficacy parameters is performed in the ITT population (main analysis), and in the PP population (additional analysis).

In case of developing acute respiratory distress syndrome and the need to switch patient to mechanical ventilation, the investigational drug is canceled, but the patient is not withdrawn from the study. Patients are under follow-up until Visit 6, the data are taken into account to assess efficacy in the ITT population.

Safety Analysis

Safety criteria

Safety assessment includes the following parameters:

- Total number of adverse events (AEs) stratified by severity and incidence;
- Incidence of adverse drug reactions;

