
Said statistical power (45%) is acceptable for exploratory stages of the studies aimed to select the duration for endpoint monitoring and to select the endpoint at the second (confirming) stage. In case change of the planned endpoints, separate adjustment will be made for the multiplicity of comparisons and the required number will be recalculated at the second stage.
 
Significance level used in the clinical study Significance levels and confidence intervals are calculated as bilateral, the statistical significance of differences is two-sided by default and refers to significance level 0.05 (unless specified otherwise).
 
Stopping criteria for the clinical study This protocol does not contain any statistical criteria for stopping the clinical study.
 
Accounting for missing data, data not to be analyzed and questionable data In the case of for missing data, data not to be analyzed and questionable data, appropriate statistical analysis methods are applied. Patients who will not be able to complete the course of therapy according to the protocol are included in the analysis of the main endpoint using the last observation carried forward (LOCF) method. This means that measures taken as criteria for efficacy will be assessed for such patients at the time of dropping out of the study.
 
Procedures for reporting any deviations from the original statistical plan All deviations from the final version of the statistical analysis plan will be described and substantiated in the final clinical study report.
 
Population analysis The statistical analysis includes the following patient populations:
 
 Safety population: patients who have received at least one dose of the study drug and for whom there is an assessment of condition and/or AE for at least one time point after administration. Population of all patients included in the study (Intent-to-treat, ITT): patients who received at least one dose of the drug in the study and for whom there is data for at least one visit after the baseline (Visit 0). Population of patients who completed the study as per the Protocol (Per protocol, PP): patients who have completed the study as per the Study Protocol. 
In case of developing acute respiratory distress syndrome and the need to switch patient to mechanical ventilation, the investigational drug is canceled, but the patient is not withdrawn
									

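### The LOCF rule treats stopping therapy as leaving the study, which conflicts with the follow-up rule for ventilated patients and gives no valid value for time to improvement

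*Combined protocol and SAP*

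**What the plan says.** All places are in the Combined protocol and SAP, section 2, Overview (Synopsis).

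- *Accounting for missing data, data not to be analyzed and questionable data.* The rule applies to "Patients who will not be able to complete the course of therapy according to the protocol". They are "included in the analysis of the main endpoint using the last observation carried forward (LOCF) method", and "measures taken as criteria for efficacy will be assessed for such patients at the time of dropping out of the study".
- *Analysis of secondary efficacy parameters*, repeated under *Safety Analysis* and *Population analysis*. If acute respiratory distress syndrome (ARDS) develops and mechanical ventilation is needed, "the investigational drug is canceled, but the patient is not withdrawn from the study". It continues: "Patients are under follow-up until Visit 6, the data are taken into account to assess efficacy in the ITT population".
- *Efficacy criteria.* There are two primary criteria: "Time (in days) to improvement in clinical status by categorical ordinal scale of clinical status improvement" and "Rate of clinical status improvement by categorical ordinal scale of clinical status improvement by 2 or more categories at Visit 3". The missing-data section speaks of one main endpoint and does not say which is meant.
- *Duration of the study.* Visit 2 is day 5, Visit 3 is day 10 and Visit 6 is day 28±1. The Arm 1 course lasts 14 days, so it runs past the day-10 endpoint.
- *Analysis of primary efficacy parameter.* ITT is the main analysis. Time to improvement is compared by t-test or Mann-Whitney test. Kaplan-Meier and log-rank-type tests are optional.

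**The concern.** The LOCF rule is triggered by one event, not completing therapy, and scored at another, leaving the study. A patient can stop the drug and remain under observation, and the synopsis says so for ventilated patients. Applied as written, the rule can replace an observed Visit 3 failure with an earlier, better status in the main ITT analysis of a primary endpoint.

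For time to improvement the problem is more basic. LOCF carries forward a status. It cannot supply the day of an event that did not happen, yet the planned t-test or Mann-Whitney test needs a number of days for every patient. No rule is given for censoring or for death.

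The trial is open-label and the text allows more than one reading. A choice made after the data are seen could change who counts as a responder.

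**Working it through.** **1. The two rules applied to one patient.** Suppose a patient is improved by two categories at Visit 2 (day 5), has the drug cancelled on day 7, and is ventilated or dead at Visit 3 (day 10).

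| Rule | Status used for Visit 3 | Result |
|---|---|---|
| LOCF, Visit 2 carried forward | Improved | Responder |
| Follow-up rule for ventilated patients | Observed on day 10 | Non-responder |

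No section says which rule takes precedence. The direct conflict is limited to ARDS with mechanical ventilation. For stops for other reasons the synopsis gives no follow-up rule, which is a gap and not a contradiction. Stops after day 10 do not matter for this endpoint, because Visit 3 has already been observed.

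**2. The plan's own sizing, as the yardstick.** The inputs under *Justification of sample size* are 65% v 80%, alpha 0.05 and target power 0.80. With unpooled variance and a one-sided test:

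n = (0.65×0.35 + 0.80×0.20) × (1.645 + 0.842)² / 0.15² = 106.5, rounded up to 107 per arm, with power 0.8017.

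This reproduces the stated figures. The planned effect is therefore 15 points; the plan then sets 100 per arm.

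**3. Size of the effect on the Visit 3 rate.** The documents state no drop-out rate, so these are assumptions:

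- d = share of one arm stopping before Visit 3
- f = fraction of those carried as improved who are not improved at Visit 3
- g = fraction of those carried as not improved who are improved at Visit 3

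Net change in that arm's rate = d × (f − g).

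Take f = 50%, g = 0, a true rate of 65% in both arms, 100 per arm and a two-sided 0.05 test (pooled variance under the null). The chance of a false win for the affected arm is Φ[(Δ − 1.96·SE₀)/SE₁], with SE₀ = √(2p̄(1−p̄)/100) and SE₁ = √((0.65×0.35 + p(1−p))/100). Here p = 0.65 + Δ, and p̄ is the mean of 0.65 and p.

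| d | Δ = d×f | SE₀ | SE₁ | Chance of a false win |
|---|---|---|---|---|
| 0 | 0 | – | – | 0.025 |
| 5% | 2.5 points | 0.0669 | 0.0668 | 0.056 |
| 10% | 5.0 points | 0.0662 | 0.0661 | 0.114 |
| 15% | 7.5 points | 0.0656 | 0.0653 | 0.207 |

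If f = g the net change is zero. If f = 0 and g = 50%, the same arm loses 2.5–7.5 points. If d, f and g are equal in both arms, the shifts cancel under the null, although both rates are misstated.

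**4. Time to improvement.** No calculation is needed to show the gap. A patient who stops on day 5 without improving could be entered as 5 days, entered as 28 days, censored on day 5 or left out. The synopsis does not choose, and these options rank the patient very differently in a Mann-Whitney test.

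**The case against.** **The ventilation rule may govern.** It is specific and is stated three times. A ventilated patient has by that rule not left the study, so there is no drop-out moment at which to score. This softens the conflict, but the LOCF trigger still names non-completion of therapy and precedence is not stated. A patient scored at the moment of ventilation would probably count as a failure. Miscounting needs Visit 2 to be carried forward, or a patient who stops for another reason while improved and then worsens.

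**A reader might infer that the bias favours Areplivir**, since only Arm 1 has a fixed 14-day course. The documents do not support this. The LOCF rule names no arm, and Arm 2 receives guideline regimens that may also go uncompleted. LOCF can also freeze as failures patients who stop early and would have recovered by day 10, which matters when 65–80% are expected to improve by then.

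**A reader might also infer that a drop-out day is entered as a fast improvement time.** The text says only that measures are assessed at drop-out; the status recorded could be not improved. A simulation shows how much rests on this reading: 4,000 trials, no true effect, 100 per arm, exponential times with mean 9 days capped at 28. If Arm 1 failures receive a drop-out day of 2–6 and Arm 2 failures receive day 28, Mann-Whitney rejects in about 13%, 36% and 65% of trials at 5%, 10% and 15% failures. With drop-out days used in both arms, it rejects in about 5%. The inflation comes from the assumed asymmetry, which the synopsis does not prescribe.

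**Fuller detail may exist elsewhere.** The synopsis refers to a final statistical analysis plan. That is possible, but the text available gives no resolution.

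**Conclusion.** The point holds in a limited form. The LOCF trigger and its scoring time do not match. The rule conflicts with the follow-up rule for ARDS with ventilation, no follow-up rule covers other stops, and LOCF has no valid meaning for time to improvement. These conclusions rest on the text and need no assumed rates.

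Neither the direction nor the size of the bias can be read from the documents. The 2.5–7.5 points, against a planned 15, assume that 5–15% of one arm stop before Visit 3, that half of them are wrongly carried as improved, and that nothing offsets this. The ordinal scale's categories are not in the text, so the ranks of ventilation and death cannot be checked.

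It still needs correcting, because two readings of a primary-endpoint rule can classify the same patient in opposite ways.

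**What to change.** Reconcile the sections so that stopping therapy does not by itself trigger LOCF. Then state the following.

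**Visit 3 rate**
- Count death or mechanical ventilation before Visit 3 as non-response.
- Otherwise use the observed Visit 3 status for every patient who has one, whether or not therapy was stopped.
- Where there is no Visit 3 record, apply one rule to both arms: status at discharge for patients discharged before day 10, and non-response for other missing status. The discharge step is needed because the synopsis moves Visit 4 to the day of discharge for Arm 2. Scoring every missing Visit 3 as failure could penalise Arm 2 patients who went home recovered.
- Keep LOCF as a sensitivity analysis.

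**Time to improvement**
- Make Kaplan-Meier with the log-rank test the main analysis.
- Keep patients who die or are ventilated before improving as not improved through day 28.
- Censor other losses at the last assessment.
- Never enter a drop-out day as an improvement time.

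**Cost.** This changes analysis wording and uses data the plan already collects. It requires no extra follow-up: where none is stated after a stop for other reasons, the missing-status rule applies. Response rates may be slightly lower than under LOCF.

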
Certified statistical software with validated algorithms is used to perform statistical analyses and to ensure proper documenting (StatSoft Statistica 10.0., IBM SPSS Statistics 22).
 
Descriptive statistics are provided for all efficacy and safety indicators collected during the study. Continuous (quantitative) data are presented using the number of observations, arithmetic mean value, confidence interval (CI) 95% for mean, standard (rms) deviation, median, interquartile span (25th and 75th centiles), minimum and maximum.
 
Ordinal, categorical and qualitative data are presented as absolute frequencies (number of observations), relative frequencies (percent) and 95% CI (unless otherwise stated).
 
The check for normality of distribution is carried out by one of the generally accepted methods (Shapiro-Wilk test, Kolmogorov-Smirnov test). For non-Gaussian distributions, non-parametric methods will be used to compare efficacy and safety indicators.
 
Significance levels and confidence intervals are calculated as bilateral, the statistical significance of differences is two-sided by default and refers to significance level 0.05 (unless specified otherwise).
 
Analysis of demographics and other source data
 
Demographic data (age, sex) and baseline condition data are presented along with summaries in the form of absolute frequencies (number of observations), relative frequencies (percent), or using the arithmetic mean, confidence interval (CI) 95% for mean, standard deviation, median, interquartile span (25th and 75th centiles), minimum and maximum, depending on the type of variable.
 
To test the study group homogeneity hypothesis, at the baseline zero hypotheses (no differences between groups) are tested with Student's t-test (for interval measures with normal distribution in the study population), Mann-Whitney's test (for ordinary measures or for interval measures with distribution different from normal) or Fisher's exact test and χ^2 test (for qualitative indicators). If statistically significant differences between study arms are found, the magnitude of differences is estimated using confidence intervals.
 
Analysis of primary efficacy parameter
 
Primary efficacy endpoints:
 
One of the primary efficacy parameters is the time (in days) to improvement of patient's clinical status according to the categorical ordinal scale of clinical improvement.
 
 • Time (in days) to improvement in clinical status on a categorical ordinal scale of clinical improvement. 
To compare the primary efficacy indicator between arms, the Student's t-test for independent samples is used. If the necessary assumptions about the normality of distribution of this indicator are not met, the non-parametric Mann-Whitney test will be used. Also, the Kaplan-Meier technique and compilation survival tables can be used as descriptive methods for studying this efficiency parameter. Gehan-Wilcoxon test, Cox-Mentel test or Log-Rank test can be used to compare the time (in days) to improve the clinical status of the patient between the study groups.
		

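### The plan has no rule for how deaths enter time to improvement or time to end of fever; its dropout rule, taken literally, turns the day of death into a time value or a censoring day

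*Combined protocol and SAP*

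**What the plan says.** All references are to the combined protocol and SAP, section 2 (Synopsis).

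- **Endpoints.** One of the two primary criteria is "Time (in days) to improvement in clinical status by categorical ordinal scale of clinical status improvement". Time to end of fever is secondary. Fatal cases are a secondary criterion of their own, compared by Fisher's exact or chi-square test.
- **Tests for the time endpoints.** Student's t-test or Mann-Whitney is named first for both. For time to improvement, Kaplan-Meier is mentioned and "survival tables can be used as descriptive methods for studying this efficiency parameter"; the Gehan-Wilcoxon, Cox-Mantel or log-rank test "can be used to compare the time (in days) to improve the clinical status of the patient between the study groups". The same optional tests "can be used to compare the time (in days) to the disappearance of fever in the study arms". No censoring rule accompanies any of them.
- **Missing data.** A general sentence says only that "appropriate statistical analysis methods are applied". Then: "Patients who will not be able to complete the course of therapy according to the protocol are included in the analysis of the main endpoint", by last observation carried forward, which the plan explains as meaning that "measures taken as criteria for efficacy will be assessed for such patients at the time of dropping out of the study". Death is not mentioned.
- **Ventilated patients.** After ARDS with a move to mechanical ventilation the study drug stops but the patient stays in the study: "Patients are under follow-up until Visit 6, the data are taken into account to assess efficacy in the ITT population". How a later death is coded is not stated.
- **Decision rule.** The primary-efficacy text accepts a statistically significant difference in time to improvement as proof of superiority.

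**The concern.** Improvement and loss of fever are favourable events that a patient who dies first can never have. The sponsor expects some deaths: they are an endpoint, and fatalities after discharge are followed by telephone. An analyst therefore has to give each death a value, and the only sentence that bears on it points to the moment of leaving the study.

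That moment can be used in two ways, both unfavourable to a fair comparison. As a number of days in a t-test or Mann-Whitney test, a death on day 6 looks like a recovery on day 6. As a censoring day in a log-rank test, it removes the patient from the risk set and assumes the same later chance of recovery as the survivors. Moving from the t-test to the log-rank test removes the first problem but not the second. In an open-label trial, leaving the choice unstated also allows it to be made after the data have been seen.

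**Working it through.** **1. The plan's own figure.** No stated figure depends on how deaths are handled. The sample-size table does reproduce: with 65% vs 80%, one-sided alpha 0.05 and unpooled variance, 0.65×0.35 + 0.80×0.20 = 0.3875; 0.15/√(0.3875/107) = 2.49; 2.49 − 1.645 = 0.85; power 0.8017, against 0.80170 stated for 107 per arm. This supplies the response rates used below.

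**2. Inputs.** From the documents: 100 per arm, follow-up to day 28, response by day 10 of 65% or 80%. Assumed, because the documents give nothing: constant hazards, and 1-10% of patients dying without prior improvement by day 28.

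**3. Overstatement by Kaplan-Meier when deaths are censored at death.** With improvement hazard λ = −ln(1 − p10)/10 and death hazard d solved to give the assumed mortality:

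- 1 − KM(t) = 1 − exp(−λt)
- cumulative incidence CIF(t) = λ/(λ+d) × [1 − exp(−(λ+d)t)]
- SE = √(CIF(1 − CIF)/100)

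Worked case, p10 = 0.65 and 5% mortality: λ = 0.105, d = 0.0058. At day 28, 1 − KM = 94.7% and CIF = 90.5%. The gap is 4.2 points; SE = 2.9 points; ratio 1.4.

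| Deaths without improvement by day 28 | Day-28 gap, points: 65% (80%) | Day-28 gap in SE | Day-10 gap in SE |
|---|---|---|---|
| 1% | 0.8 (1.0) | 0.35 (0.67) | 0.06 (0.12) |
| 2% | 1.7 (1.9) | 0.66 (1.1) | 0.13 (0.24) |
| 5% | 4.2 (4.8) | 1.4 (2.0) | 0.32 (0.59) |
| 10% | 8.5 (9.6) | 2.5 (3.1) | 0.65 (1.2) |

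If the 5% is instead read as the risk of death in the absence of improvement, the day-28 gap falls to about 0.55-0.73 SE.

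**4. Log-rank comparison, deaths censored at death or kept as not improved to day 28.** Simulated with 100 per arm and equal improvement hazards; negative z is against the arm with more deaths.

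- 70% improved by day 10, deaths 8% vs 2%: mean z 0.00 censored, −0.80 kept. A separate run gave 0.00 and −0.87.
- Median 9 days to improvement, deaths 10% vs 2%: −0.01 censored, −0.76 kept. Kaplan-Meier shows 0.885 vs 0.883 improved by day 28; the shares that really improved are 0.816 vs 0.870.
- Same, deaths 20% vs 5%: 0.03 censored, −1.37 kept.
- If those who die would never have improved, part of the penalty survives censoring: −0.52 against −1.15 (10% vs 2%), −1.03 against −2.05 (20% vs 5%).

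**5. Day of death used as the time value.** Take equal improvement hazards h = ln 2/9 = 0.077, with survivors who have not improved set to day 28. The mean recorded time is [1 − exp(−28(h+d))]/(h+d). With 10% deaths (d = 0.0095) this is 10.53 days; with 2% (d = 0.0018) it is 11.29. The arm with more deaths looks 0.76 days faster although recovery is the same. Simulation in whole days gave 0.72 days, and 1.48 days at 20% vs 5%. If those who die would never have improved, the apparent gain nearly vanishes (0.06 days at 10% vs 2%), but the extra deaths still cost that arm nothing.

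**The case against.** The strongest reply is that the plan nowhere says deaths are censored or given the day of death. The missing-data text names last observation carried forward, and carrying forward a status of not improved could equally mean that the dead remain not improved, which is the right answer. That ambiguity is real, so censoring at death is an inference and not a planned step. It does not remove the need for a rule, because the explanatory sentence fixes the assessment at the time of leaving and supplies no number of days for someone who never improves.

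Other points also stand:

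- The carry-forward sentence covers only the main endpoint and only patients unable to complete the course. It does not reach end of fever, and may not reach a death after the 14-day course.
- It is not the only rule for early stoppers: ventilated patients are followed to Visit 6.
- The survival methods are optional, so the censoring problem arises only if they are chosen. Under the tests named first, the problem is the one in step 5.
- The size rests on assumed mortality. Enrolment is limited to medium severity with need for intensive care excluded, day-28 Kaplan-Meier is not a named endpoint, and the day-10 shift is small. With equal mortality (3% each) the log-rank comparison does not move. Even at 2% vs 8%, the kept-to-day-28 analysis passes |z| > 1.96 in only about 13% of trials.
- The categories of the ordinal scale are not shown, so whether death is its worst category cannot be checked.

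A reader might infer that excess deaths never count against an arm in this trial. The documents do not support that. Fatal cases, intensive-care transfer and ventilation are each compared separately; 10 vs 2 deaths per 100 gives Fisher p = 0.033. In the other primary endpoint, a patient in the ITT population who dies without a prior 2-category gain can count as a non-responder at Visit 3. The concern is confined to the two time endpoints.

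**Conclusion.** The point holds in this limited form. Death precludes both time endpoints, the plan does not say how it enters them, and the one sentence that bears on the primary endpoint points to the day of leaving without excepting death. Since a significant time difference is accepted as proof of superiority, a separate secondary mortality comparison does not repair this.

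At an assumed 2-5% dying without improvement, censoring at death overstates the day-28 share improved by about 2-5 points (0.7-2.0 SE), and by at most about 0.6 SE at day 10. At an assumed 2% vs 8%, it moves the mean log-rank z from about −0.8 to about 0. These figures assume constant hazards and, for the full loss of the penalty, that those who die had the survivors' chance of recovery; if they would never have improved, roughly half the penalty remains. With equal mortality in the arms the comparison is essentially unaffected. The change is worth making because it is cheap and prevents an avoidable bias, not because a large effect has been shown.

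**What to change.** Add to the primary-efficacy, secondary-efficacy and missing-data parts of the synopsis and SAP:

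- For time to improvement and time to end of fever, a patient who dies without the event is kept as not having reached it through day 28: censored at day 28 in the log-rank test, given the worst rank in the Mann-Whitney test, and never given the day of death as the time value.
- Curves are shown as cumulative incidence, with death as a competing event.
- Carry-forward does not apply to deaths.

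The cost is a few sentences and a recode of the time variable for deaths. No new data are needed, since fatalities are already followed by telephone after discharge, and the named log-rank and Mann-Whitney tests can stay. The downside is that the reported share improved by day 28 becomes slightly lower.
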